### 5.3.1 Inclusion Criteria

1. Signed written informed consent.
2. Chinese men or women  $\geq$  18 years of age.
3. Availability of a recently obtained FFPE block containing tumor tissue (biopsy from a non-irradiated area within 6 months) or 12 or more unstained tumor slides suitable for biomarker detection (see Section 7.6).
4. Histologically or cytologically proven locally advanced unresectable or metastatic solid tumor, for which no standard therapy exists or standard therapy has failed.
5. ECOG performance status of 0 or 1 at study entry.
6. Estimated life expectancy of at least 3 months.
7. Adequate hematological function as defined below:

- White blood cell count  $\geq 3 \times 10^9/L$
  - Absolute neutrophil count  $\geq 1.5 \times 10^9/L$
  - Lymphocyte count  $\geq 0.5 \times 10^9/L$
  - Platelet count  $\geq 100 \times 10^9/L$
  - Hemoglobin  $\geq 90$  g/L (may have been transfused).
8. Adequate liver function as defined below:
- Total bilirubin  $\leq 1.5 \times$  upper limit of normal (ULN)
  - Aspartate aminotransferase (AST)  $\leq 2.5 \times$  ULN
  - Alanine aminotransferase (ALT)  $\leq 2.5 \times$  ULN.
9. Adequate renal function as defined below:
- Estimated creatinine clearance  $\geq 50$  mL/min according to Cockcroft-Gault formula.
10. Negative blood pregnancy test at Clinical Screening for women of childbearing potential. For the purposes of this study, women of childbearing potential are defined as: All female subjects after puberty unless they have age-related natural (spontaneous) amenorrhea  $\geq 12$  consecutive months and increased follicle-stimulating hormone (FSH)  $> 40$  mIU/mL, are surgically sterile, or are sexually inactive.
11. Highly effective contraception (ie, methods with a failure rate of less than 1% per year) for both men and women if the risk of conception exists. See Section 12, Appendix III for further guidance on methods of contraception that are considered highly effective.

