Grade 2 AST or ALT > 3.0 to ≤ 5 × ULN and/or total bilirubin > 1.5 to ≤ 3 × ULN	Withhold avelumab therapy Increase frequency of monitoring to every 3 days	If returns to Grade ≤ 1: Resume routine monitoring; resume avelumab therapy If elevation persists > 5 to 7 days or worsens: Treat as Grade 3 to 4
Grade 3 to 4 AST or ALT > 5 × ULN and /or total bilirubin > 3 × ULN	Permanently discontinue avelumab therapy Increase frequency of monitoring to every 1 to 2 days 1.0 to 2.0 mg/kg/day prednisone or equivalent Add prophylactic antibiotics for opportunistic infections Consult gastroenterologist/hepatologist Consider obtaining MRI/CT scan of liver and liver biopsy if clinically warranted	If returns to Grade ≤ 1: taper steroids over at least 1 month If does not improve in > 3 to 5 days, worsens or rebounds: add mycophenolate mofetil 1 g twice daily If no response within an additional 3 to 5 days, consider other immunosuppressants per local guidelines
Renal irAEs		
Grade of Creatinine Increased (NCI-CTCAE v4.03)	Initial Management	Follow-up Management
Grade 1 Creatinine increased > ULN to 1.5 × ULN	Continue avelumab therapy	Continue renal function monitoring If worsens: Treat as Grade 2 to 3 or 4
Grade 2 to 3 Creatinine increased > 1.5 and ≤ 6 × ULN	Withhold avelumab therapy Increase frequency of monitoring to every 3 days 1.0 to 2.0 mg/kg/day prednisone or equivalent. Add prophylactic antibiotics for opportunistic infections Consider renal biopsy	If returns to Grade ≤ 1: Taper steroids over at least 1 month, and resume avelumab therapy following steroids taper. If worsens: Treat as Grade 4.
Grade 4 Creatinine increased > 6 × ULN	Permanently discontinue avelumab therapy Monitor creatinine daily 1.0 to 2.0 mg/kg/day prednisone or equivalent. Add prophylactic antibiotics for opportunistic infections Consider renal biopsy Nephrology consult	If returns to Grade ≤ 1: Taper steroids over at least 1 month
Cardiac irAEs		
Myocarditis	Initial Management	Follow-up Management

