15.3 Clinical Laboratory Evaluation

All laboratory assessments are performed at local laboratories and comply with local requirements.

Laboratory values (including corresponding normal ranges) from local laboratories will be converted into the standard units by data management. The results in standard units will be used for the analyses.

Laboratory results will be classified according to the NCI-CTCAE toxicity grading version 4.03. If toxicities for high and low values of a specific parameter are defined, these toxicities will be analyzed separately for the parameter as “Parameter low” and “Parameter high” (appendix 18.3).

Laboratory results that are not part of the NCI-CTCAE will be presented according to the categories: below normal limits, within normal limits and above normal limits (according to the local laboratories normal ranges).

- **Hematology:** Hematocrit, Hemoglobin, Platelet count, Red blood cells (RBC) count, White Blood Cell Count, Absolute lymphocytes count, Lymphocytes, Absolute Neutrophils count, Neutrophils, Absolute monocyte count, Monocytes, Absolute eosinophil count, Eosinophils, Absolute basophil count, Basophils, RBC morphology, Absolute reticulocytes count, Reticulocytes, Mean corpuscular hemoglobin (MCH), Mean corpuscular volume (MCV), Mean corpuscular hemoglobin concentration (MCHC).
- **Hemostaseology:** Activated partial thromboplastin time (aPTT), Prothrombin time (PT), International Normalized Ratio (INR).
- **Biochemistry:** Albumin, Alkaline phosphatase, Alanine Aminotransferase (ALT), Amylase, Aspartate Aminotransferase (AST), Gamma Glutamyl Transpeptidase (GGT), Blood Urea Nitrogen (BUN), Urea, Calcium, Chloride, Cholesterol, Creatine kinase, Creatinine, C-Reactive Protein (CRP), Glucose, Lactate dehydrogenase (LDH), Lipase, Phosphorus, Magnesium, Potassium, Sodium, Total bilirubin, Protein total, Uric acid, Triglycerides, Hemoglobin A1c.
- **Hormonal tests:** Free Thyroxine (T4), Thyroid-Stimulating Hormone (TSH), Follicle-stimulating hormone.
- **Urinalysis:** pH, Specific gravity, Protein content, Sediment analysis, Albumin, Immunoglobulin G.

NCI-CTCAE grades available:

The laboratory toxicities will be tabulated by the worst on-treatment CTCAE grade or the shift of CTCAE grade from baseline to worst grade during on-treatment period using descriptive statistics (count and percentage). The highest CTCAE grade during the on-treatment period is considered as the worst grade for the summary.

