- The worst grade during the on-treatment period will be summarized considering only patients with post baseline laboratory samples: Laboratory tests by NCI-CTCAE grade (0, 1, 2, 3, 4, and missing).

The shift table will summarize baseline CTCAE grade vs. the worst on-treatment CTCAE grade (grade = 0, 1, 2, 3, 4, missing). The above analyses apply to the following hematology and biochemistry parameters which can be graded per NCI-CTCAE:

- Hematology: Hemoglobin, Lymphocytes, Neutrophils, Platelets, White Blood Cell.

- Biochemistry: Creatinine, Alanine Aminotransferase, Aspartate Aminotransferase, Gamma Glutamyl Transferase, Total Bilirubin, Lipase, Amylase, Albumin, Alkaline Phosphatase, Glucose, Uric Acid, Sodium, Potassium, Calcium, Magnesium, Cholesterol, Creatine kinase, Triglyceride, Phosphorus.

Tables will summarize, separately for hematology and biochemistry parameters, the shift from baseline grade to worst on-treatment grade by parameters and dose level.

NCI-CTCAE grades not available:

The worst on-treatment value for hematology and biochemistry parameters which cannot be graded per NCI-CTCAE will be summarized by parameter according to the local laboratories normal ranges as follows:

- Shift from baseline value (low, normal, high) to above normal during on-treatment period
- Shift from baseline value (low, normal, high) to below normal during on-treatment period.

The above analyses apply to the following hematology and biochemistry parameters which cannot be graded per NCI-CTCAE:

- Hematology: Hematocrit, Red Blood Cells, RBC morphology, Monocytes, Eosinophils, Basophils, Reticulocytes, MCH, MCV, MCHC.
- Biochemistry: Total Protein, Blood Urea Nitrogen, Blood Urea, Chloride, C-Reactive Protein (CRP), Glucose, Lactate dehydrogenase, Hemoglobin A1c.

Quantitative data will also be examined for trends using descriptive statistics (n, missing, mean, SD, median, Q1, Q3, minimum, and maximum) of actual values, absolute changes and percent changes from baseline to each visit over time. This summarization will apply to hematology and chemistry parameters with numeric results assessed at baseline, post-baseline, discontinuation, end of treatment, and safety follow-up visits.

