Listing of clinically significant hematology values and listing of clinically significant biochemistry values will also be provided. Clinically significant values are defined as values with associated NCI-CTCAE grade greater or equal to 3. The following information will be included in those listings:

- Selected dosing information: date of first/last administration
- Laboratory parameter with unit
- Visit of laboratory parameter measurement
- Collection date of laboratory parameter
- Value of laboratory parameter
- Local laboratories normal ranges for laboratory parameter (lower limit of normal and upper limit of normal)

- Normal range indicator for value of the laboratory parameter (Low, Normal, High)
- Associated grade for value of the laboratory parameter according to NCI-CTCAE if applicable.

Other laboratory parameters

The following laboratory parameters collected in the CRF will be presented in specific listing presenting all collected data-fields in the CRF.

- Hemostaseology: Activated partial thromboplastin time (aPTT), Prothrombin time (PT), International Normalized Ratio (INR)
- Hormone: Free T4 and TSH
- Urinalysis: all urinalysis parameters
- Pregnancy test
- Serology

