18.3 CTCAE Toxicities of Laboratory Evaluations

Laboratory Evaluation	Toxicity	Grade	Value
Albumin	LOW	1	<LLN - 30 g/L
	LOW	2	<30 - 20 g/L
	LOW	3	<20 g/L
Alkaline Phosphatase	HIGH	1	>1.0 - 2.5 x ULN
	HIGH	2	>2.5 - 5.0 x ULN
	HIGH	3	>5.0 - 20.0 x ULN
	HIGH	4	>20.0 x ULN
Alanine Aminotransferase	HIGH	1	>1 - 3.0 x ULN
	HIGH	2	>3 - 5.0 x ULN
	HIGH	3	>5 - 20.0 x ULN
	HIGH	4	>20 x ULN
Aspartate Aminotransferase	HIGH	1	>1 - 3.0 x ULN
	HIGH	2	>3 - 5.0 x ULN
	HIGH	3	>5 - 20.0 x ULN
	HIGH	4	>20 IU/L
Calcium	HIGH	1	> ULN - 2.9 mmol/L;
	HIGH	2	>2.9 - 3.1 mmol/L;
	HIGH	3	>3.1 - 3.4 mmol/L
	HIGH	4	>3.4 mmol/L
	LOW	1	< LLN - 2.0 mmol/L
	LOW	2	<2.00 - 1.75 mmol/L
	LOW	3	<1.75 - 1.5 mmol/L
	LOW	4	<1.50 mmol/L
Cholesterol	HIGH	1	>ULN - 7.75 mmol/L
	HIGH	2	>7.75 - 10.34 mmol/L
	HIGH	3	>10.34 - 12.92 mmol/L
	HIGH	4	>12.92 mmol/L
Creatine Kinase	HIGH	1	>1.0 - 2.5 x ULN
	HIGH	2	>2.5 - 5 x ULN
	HIGH	3	>5.0 - 10 x ULN
	HIGH	4	>10.0 x ULN
Creatinine	HIGH	1	>1.0 - 1.5 x ULN
	HIGH	2	>1.5 - 3.0 x ULN
	HIGH	3	>3.0 - 6.0 x ULN
	HIGH	4	>6.0 x ULN
Gamma Glutamyl Transferase	HIGH	1	>1.0 - 2.5 x ULN
	HIGH	2	>2.5 - 5.0 x ULN
	HIGH	3	>5.0 - 20.0 x ULN
	HIGH	4	>20.0 x ULN
Glucose	HIGH	1	>ULN - 8.9 mmol/L
	HIGH	2	>8.9 - 13.9 mmol/L
	HIGH	3	>13.9 - 27.8 mmol/L
	HIGH	4	>27.8 mmol/L
	LOW	1	< LLN - 3.0 mmol/L
	LOW	2	<3.0 - 2.2 mmol/L
	LOW	3	<2.2 - 1.7 mmol/L
LOW	4	<1.7 mmol/L	

Laboratory Evaluation	Toxicity	Grade	Value
Hemoglobin	HIGH	1	> ULN - ULN + 20 g/L
	HIGH	2	> ULN + 20 - ULN + 40 g/L
	HIGH	3	> ULN + 40 g/L
	LOW	1	< LLN - 100 g/L
	LOW	2	<100.0 - 80 g/L
	LOW	3	<80.0 g/L
Lipase	HIGH	1	>1.0 - 1.5 x ULN
	HIGH	2	>1.5 - 2.0 x ULN
	HIGH	3	>2.0 - 5.0 x ULN
	HIGH	4	>5.0 x ULN
Lymphocytes	HIGH	2	>4.00 - 20.00 10 ⁹ /L
	HIGH	3	>20.00 10 ⁹ /L
	LOW	1	< LLN - 0.8 10 ⁹ /L
	LOW	2	<0.80 - 0.5 10 ⁹ /L
	LOW	3	<0.50 - 0.2 10 ⁹ /L
Magnesium	LOW	4	<0.20 10 ⁹ /L
	HIGH	1	>ULN - 1.23 mmol/L
	HIGH	3	>1.23 - 3.30 mmol/L
	HIGH	4	>3.30 mmol/L
	LOW	1	< LLN - 0.5 mmol/L
	LOW	2	<0.50 - 0.4 mmol/L
	LOW	3	<0.40 - 0.3 mmol/L
Neutrophils	LOW	4	<0.30 mmol/L
	LOW	1	< LLN - 1.5 10 ⁹ /L
	LOW	2	<1.50 - 1.0 10 ⁹ /L
	LOW	3	<1.00 - 0.5 10 ⁹ /L
Phosphate; Phosphorus	LOW	4	<0.50 10 ⁹ /L
	LOW	1	< LLN - 0.8 mmol/L
	LOW	2	<0.80 - 0.6 mmol/L
	LOW	3	<0.60 - 0.3 mmol/L
Platelets	LOW	4	<0.30 mmol/L
	LOW	1	< LLN - 75.0 10 ⁹ /L
	LOW	2	<75 - 50.0 10 ⁹ /L
	LOW	3	<50 - 25.0 10 ⁹ /L
Potassium	LOW	4	<25 10 ⁹ /L
	HIGH	1	>ULN - 5.5 mmol/L
	HIGH	2	>5.5 - 6.0 mmol/L
	HIGH	3	>6.0 - 7.0 mmol/L
	HIGH	4	>7.0 mmol/L
	LOW	2	< LLN - 3.0 mmol/L

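### SAP Appendix 18.3 sets AST Grade 4 at an absolute 20 IU/L instead of a multiple of ULN, so the band overlaps Grades 1 to 3 and can reach into the normal range

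*SAP*

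**What the plan says.** SAP Section 15.3 names the grading standard: "Laboratory results will be classified according to the NCI-CTCAE toxicity grading version 4.03". Its next sentence, on analysing low and high toxicities separately, points to Appendix 18.3, which gives the numeric cut-offs. According to the SAP's modification history, that appendix was added in Final 2.0.

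AST is one of the graded biochemistry parameters; the list begins "Creatinine, Alanine Aminotransferase, Aspartate Aminotransferase, Gamma Glutamyl Transferase, Total Bilirubin". For the worst-grade and shift tables, "The highest CTCAE grade during the on-treatment period is considered as the worst grade for the summary". For the listing, "Clinically significant values are defined as values with associated NCI-CTCAE grade greater or equal to 3".

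In Appendix 18.3 the block headed "Aspartate Aminotransferase" has four rows: above 1 to 3.0 x ULN (Grade 1), above 3 to 5.0 x ULN (Grade 2), above 5 to 20.0 x ULN (Grade 3) and above 20 IU/L (Grade 4). The ALT block has the same first three rows, and its Grade 4 is above 20 x ULN. GGT and alkaline phosphatase also start Grade 4 at 20.0 x ULN.

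Protocol Table 6-2, which labels its liver grades as NCI-CTCAE v4.03, defines the hepatic Grade 3 to 4 category as "AST or ALT > 5 × ULN and /or total bilirubin > 3 × ULN".

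**The concern.** One cell changes from a relative to an absolute scale partway through a single grading ladder. It is the only entry in the appendix expressed in IU/L, and nothing elsewhere in the SAP or protocol corrects it. Grade 3 ends at 20 x ULN, so Grade 4 should begin there. A threshold of 20 IU/L instead sits at the bottom of the ladder, or below it.

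Three outputs use the grade: the AST worst-grade table, the AST shift table and the listing of values at Grade 3 or above. If the cell were coded as printed, subjects with unremarkable AST could appear at the most severe laboratory grade. A subject already at Grade 4 at baseline could not show an upward shift if AST later rose. Protocol Section 3.2.1 names autoimmune hepatitis among the important risks of avelumab, so AST tables are ones a safety reader will look at.

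**Working it through.** **Inputs.** The AST and ALT bands come from SAP Appendix 18.3. The entry limit for AST, 2.5 x ULN, is inclusion criterion 8 in Protocol Section 5.3.1. The ULN is not stated, because "All laboratory assessments are performed at local laboratories and comply with local requirements". I assume 25 to 50 IU/L and add 15 and 20 IU/L as stress cases.

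**Step 1: can the printed figure be reproduced?** Grade 4 should start where Grade 3 stops, at 20 x ULN. Setting 20 x ULN = 20 IU/L gives ULN = 1 IU/L. So the printed cut-off matches the rest of the ladder only for a ULN of 1 IU/L, far below any value considered here.

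**Step 2: where does 20 IU/L fall?** Printed cut-off as a multiple of ULN = 20 / ULN. Cut-off implied by the ladder = 20 x ULN. Entry limit = 2.5 x ULN.

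| Assumed ULN (IU/L) | 20 / ULN | Normal values that meet printed Grade 4 (IU/L) | 20 x ULN (IU/L) | 2.5 x ULN (IU/L) |
|---|---|---|---|---|
| 15 | 1.33 | none | 300 | 37.5 |
| 20 | 1.00 | none | 400 | 50 |
| 25 | 0.80 | above 20, up to 25 | 500 | 62.5 |
| 30 | 0.67 | above 20, up to 30 | 600 | 75 |
| 40 | 0.50 | above 20, up to 40 | 800 | 100 |
| 50 | 0.40 | above 20, up to 50 | 1,000 | 125 |

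**Step 3: overlap with Grades 1 to 3.** For any ULN of 20 IU/L or more, Grades 1 to 3 lie wholly above 20 IU/L, so every value in them also meets the printed Grade 4. At a ULN of 15 IU/L, Grade 1 runs from 15 to 45 IU/L and overlaps from 20 IU/L upward; Grades 2 (45 to 75) and 3 (75 to 300) overlap completely. The bands therefore clash at every ULN tried.

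**Step 4: effect on a single value.** Take ULN = 40 IU/L.
- AST 30 IU/L is 30 / 40 = 0.75 x ULN. It meets no row except the printed Grade 4. With Grade 4 at 20 x ULN it is Grade 0.
- AST 250 IU/L is 250 / 40 = 6.25 x ULN. It meets both Grade 3 and the printed Grade 4. With the corrected cell it is Grade 3 only.

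The SAP gives no rule for a value that meets two bands. If the higher grade is taken, a subject going from 30 to 250 IU/L is tabulated as Grade 4 to Grade 4, with no shift. If the lower grade is taken, the same subject appears to improve from Grade 4 to Grade 3. With the corrected cell the shift is Grade 0 to Grade 3.

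**Step 5: after correction.** With Grade 4 above 20 x ULN, values at or below ULN are Grade 0, and Grades 0 to 4 are contiguous and all reachable at every ULN in the table.

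**The case against.** The strongest reply is that Section 15.3 makes NCI-CTCAE v4.03 the standard and cites the appendix only in parentheses. A programmer working from the published criteria would not use this cell at all, and the documents show no grading program or output. That stands as a limit on the conclusion: the effect is conditional on literal use of the appendix. It does not remove the defect, because the SAP then carries a named standard and a lookup row whose neighbours contradict it, and validation against the appendix would reproduce the error.

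A second reply is that errors would be noticed. The listing shows the value, the local normal range and a low/normal/high indicator beside the grade, and Section 15.3 also summarises actual values and changes by visit. This also stands: a real AST rise would remain visible outside the grade-based tables.

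Three stronger readings are tempting and are not supported.
- A reader might infer that most subjects would be coded Grade 4. The documents give no AST distribution and no ULN, so no proportion can be stated.
- A reader might infer that the worst-grade rule forces Grade 4 wherever bands overlap. That rule selects the highest grade over the on-treatment period; it does not say how to grade one value that meets two bands. Only values above 20 IU/L and at or below ULN meet Grade 4 alone.
- A reader might infer that key safety endpoints are compromised. Dose-limiting toxicities are taken from the adverse event form (SAP Section 15.1), adverse event severity is graded by the investigator (Section 15.2), and immune-related events are identified from preferred terms and case report form answers (Appendix 18.2).

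**Conclusion.** Wrong as written. The AST Grade 4 entry contradicts the AST Grade 3 limit, the ALT row and Protocol Table 6-2. The unit inconsistency and the overlap with Grades 1 to 3 are plain from the appendix, and the overlap appears at every ULN from 15 to 50 IU/L. The coding of normal values as Grade 4 rests on two conditions: literal use of the appendix, and a local ULN above 20 IU/L. At an assumed ULN of 25 to 50 IU/L the printed cut-off is 25 to 50 times lower than the one the ladder implies (20 x ULN / 20 = ULN). The reach is limited to the AST worst-grade table, the AST shift table and the AST entries in the listing of values at Grade 3 or above. Whether any output has been produced with this cell cannot be seen from the documents.

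**What to change.** In SAP Appendix 18.3, change AST Grade 4 from above 20 IU/L to above 20 x ULN. This follows from the upper limit of AST Grade 3 and from the ALT row, so it needs no outside source. Confirm that the grading program uses the corrected threshold. The cost is one table cell and one program check. No endpoint, sample size or clinical procedure changes.

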**Statistical methods:**

The sample size estimated for the study is not based on any statistical assumptions. Rather, it follows the “3 + 3” rule, a well-established methodology for the design of dose-finding studies in oncology.

For the primary endpoints, the number and proportion of subjects experiencing DLTs will be reported by dose level (excluding 10 mg/kg once weekly cohort). Pharmacokinetic parameters will be summarized using descriptive statistics. The point estimate of ORR/median DOR and 95% CIs will be calculated.

The primary analysis, including all endpoints analyses, for study data will be conducted at the time when all subjects complete PK sample collection (including all samples collected if the

treatment discontinued earlier than Week 13). The data cutoff time point for primary analysis is set at Week 13 (Day 85) of the last subject.

The data from primary analysis will be summarized in the Clinical Study Report (CSR).

The final analysis of study data will be conducted after End of Study, which is defined as the last patient complete 90-day Safety Follow-up Phone Call or last patient died, whichever comes first. Additional data from primary analysis up to this cutoff date will be analyzed and presented as an addendum of CSR.

Table 1-1 Schedule of Assessments for Subjects Receiving Avelumab Once Every 2 Weeks

Assessment	Clinical Screening / Baseline Assessments	Treatment Phase 								EOT Visit 	Safety Follow-up 	Long-term Follow-up 	
		≤ Day -14 to Day -1	V1	V2	V3	V4	V5	V6	V7				Until progression
			W1	W3	W5	W7	W9	W11	W13				
			D1	D15	D29	D43	D57	D71	D85				
CCI													
Written informed consent	X												
Inclusion/exclusion criteria	X												
Medical history 	X												
Demographic data	X												
Hepatitis B, hepatitis C, and HIV tests	X												
Full physical examination 	X									X	X		

Assessment	Clinical Screening / Baseline Assessments	Treatment Phase 								EOT Visit 	Safety Follow-up 	Long-term Follow-up 	
		≤ Day -14 to Day -1	V1	V2	V3	V4	V5	V6	V7				Until progression
			W1	W3	W5	W7	W9	W11	W13				
			D1	D15	D29	D43	D57	D71	D85				
Symptom-directed physical exam 		As indicated throughout the Treatment Phase											
Height	X												
Vital signs	X	X	X	X	X	X	X	X	2-weekly	X	X		
Weight	X	X	X	X	X	X	X	X	2-weekly	X	X		

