### **Abnormal Laboratory Findings and Other Abnormal Investigational Findings**

Abnormal laboratory findings and other abnormal investigational findings (eg, on an ECG trace) should not be reported as AEs unless they are associated with clinical signs and symptoms, lead to treatment discontinuation or are considered otherwise medically important by the Investigator. If an abnormality fulfils these criteria, the identified medical condition (eg, anemia, increased ALT) must be reported as the AE rather than the abnormal value itself.

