#### 8.3.3 Safety Endpoints

In addition to the endpoints specified as primary and secondary endpoints, laboratory parameters will be evaluated.

CCI

CCI

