### 8.5.3 Analysis of Secondary and Safety Endpoints

#### 8.5.3.1 Analysis of Safety Endpoints

The extent of exposure to avelumab will be characterized by duration (weeks), number of administrations, cumulative dose (mg/kg), dose intensity (mg/kg/week), relative dose intensity (actual dose given/planned dose), number of dose reductions, and number of dose delays.

Safety analyses will be performed on the Safety Analysis Set. The safety endpoints will be tabulated by dose level and cohort, using descriptive statistics.

Safety assessments will be based on review of the incidence of AEs, ADRs, and changes in vital signs, ECGs, body weight, and laboratory values (hematology and serum chemistry).

The on treatment period is defined as the time from the first administration of avelumab to the last administration of avelumab date plus 30 days or the earliest date of subsequent anticancer drug therapy minus 1 day, whichever occurs first.

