## Laboratory Variables

Laboratory results will be classified by grade according to NCI-CTCAE v4.03. The worst on study grades after the first administration of avelumab will be summarized. Shifts in toxicity grading from first treatment to highest grade will be displayed. Results for variables that are not part of NCI-CTCAE will be presented as below, within, or above normal limits. Only subjects with postbaseline laboratory values will be included in these analyses.

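### SAP 15.3 gives TSH and free T4 a listing only, although the protocol and the SAP's own opening rule call for low/normal/high presentation of results outside NCI-CTCAE

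*SAP*

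**What the plan says.** Protocol 8.3.3 adds to the primary and secondary endpoints that "laboratory parameters will be evaluated", with no limit by panel. Protocol 8.5.3.1 says "The safety endpoints will be tabulated by dose level and cohort, using descriptive statistics". Its Laboratory Variables paragraph grades results by NCI-CTCAE and, for the rest, states: "Results for variables that are not part of NCI-CTCAE will be presented as below, within, or above normal limits".

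SAP 15.3 opens with the same rule: "Laboratory results that are not part of the NCI-CTCAE will be presented according to the categories" of low, normal and high against the local ranges. Directly below, it names five groups of tests, among them hemostaseology (aPTT, PT, INR) and hormonal tests (free T4, TSH, FSH). The detailed paragraphs that follow confine the grade summaries, the low/normal/high shift summaries and the by-visit statistics to hematology and biochemistry. At the end of the section, under Other laboratory parameters, hemostaseology and free T4/TSH "will be presented in specific listing presenting all collected data-fields in the CRF".

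SAP Appendix 18.3 has no grading row for any of these five tests. SAP Section 7 declares one change from the protocol, on biomarkers.

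**The concern.** The SAP states a rule for results outside NCI-CTCAE and then, in the same section, gives TSH and free T4 an output that does not meet it. The reader of the study report would have no by-cohort count of subjects whose thyroid tests moved out of range.

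This matters more for the thyroid than for most panels. Protocol 3.2.1 lists hypothyroidism, hyperthyroidism and thyroiditis among the immune-mediated reactions identified as important risks. Table 1-1 schedules free T4 and TSH at screening, Days 43 and 85, 6-weekly after that, at the EOT Visit and at the 30-day visit. The study is meant to support a China submission (protocol 3.3) and a comparison of safety across studies, including ethnic sensitivity (protocol 5.2.2). That comparison needs counts by dose level and cohort.

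The AE tables do not close the gap fully, because protocol 7.4.1.1 keeps some abnormal laboratory values out of AE reporting.

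**Working it through.** There is no design figure to reproduce. The protocol synopsis says "The sample size estimated for the study is not based on any statistical assumptions", and no error rate or power bears on this point. The check is a comparison of text.

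**Step 1. Where each test is summarised in SAP 15.3**

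| Summary type | Scope in SAP 15.3 | TSH, free T4 | aPTT, PT, INR |
|---|---|---|---|
| Worst on-treatment CTCAE grade | named hematology and biochemistry | no | no |
| Shift in CTCAE grade | same list | no | no |
| Low/normal/high shift | named hematology and biochemistry without grades | no | no |
| By-visit descriptive statistics | hematology and chemistry | no | no |
| Listing of CRF fields | Other laboratory parameters | yes | yes |

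Result: 0 of 4 summary types. (FSH is named in SAP 15.3 but has no output assigned. It is drawn only at screening, so no shift table applies to it.)

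**Step 2. Is this a small-sample choice?** The parameters that do get a grade or low/normal/high table are 5 hematology + 19 biochemistry (graded) + 10 hematology + 8 biochemistry (ungraded) = 42 entries. Glucose is counted twice because it stands in both biochemistry lists. MCH, MCV and reticulocytes are included. At the same sample size the SAP tabulates these and leaves out the thyroid tests.

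**Step 3. Does a listing satisfy the rule?** Protocol 8.5.1 already requires individual listings of all recorded data. If a listing were enough, the low/normal/high sentence would add nothing. Nor does SAP 15.3 ask for a low/normal/high indicator in this listing. It asks for one only in the listings of hematology and biochemistry values of grade 3 or above.

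**Step 4. What can still reach a table through AEs?** Protocol 7.4.1.1 says abnormal laboratory findings "should not be reported as AEs unless they are associated with clinical signs and symptoms". The sentence continues with two further triggers: treatment discontinuation, or medical importance in the Investigator's view. When any trigger is met, the medical condition is reported as an AE. If treatment-emergent, it enters the tables of SAP 15.2.1. It also enters the irAE tables by dose level/cohort (SAP 15.2.5) if it meets Appendix 18.2, which requires, among other criteria, that corticosteroids, immunosuppressants or hormonal therapy were given. What remains outside every table is a TSH or free T4 shift that meets none of the three triggers.

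**Step 5. Coagulation.** The low/normal/high rule covers only variables outside NCI-CTCAE. Appendix 18.3 omits aPTT, PT and INR, but neither document says whether they are gradable. If they are, the rule missed is grading. If not, it is low/normal/high. In both cases they reach no table.

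**The case against.** The sponsor's best reply is that the protocol is not breached. The Laboratory Variables sentence says results are presented, not tabulated. Protocol 8.5.3.1 describes the safety review as covering "laboratory values (hematology and serum chemistry"), which is the set the SAP tabulates. Protocol 8.5.1 leaves full details to the SAP. This has some force, and it makes the conflict firmest inside the SAP, between the opening rule of 15.3 and its later paragraphs. It does not remove the point. Protocol 8.3.3 names laboratory parameters without restriction, 8.5.3.1 itself says safety endpoints are tabulated, and listings were already required for everything.

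A second reply is that thyroid toxicity is captured as AEs. For many cases it is. A reader might infer that asymptomatic thyroid toxicity appears in no table, or that no thyroid rate can be read by cohort. The documents do not support either. An abnormality without symptoms that the Investigator judges medically important, or that stops treatment, is an AE and is counted. Protocol 7.4.4 also asks for newly diagnosed or worsening conditions to be reported as AEs.

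Third, no data are lost. Every result is listed, and with about 24 subjects at most the shifts could be counted by hand. That is true, but it leaves to the reader a count that the plan's own rule assigns to the analysis.

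Finally, laboratory parameters are neither primary nor secondary endpoints, and no escalation, DLT or PK result depends on this table. That stands and limits the weight of the point.

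**Conclusion.** The point holds in a limited form. SAP 15.3 gives TSH and free T4 a listing only, against protocol 8.5.3.1 and its own opening rule, without a declared change in Section 7. In consequence, thyroid laboratory shifts not reported as AEs appear in no summary table by cohort, although thyroid events are a named important risk.

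The size is two thyroid tests, plus three coagulation tests with an unsettled rule, absent from all 4 laboratory summary types for all subjects. How many shifts go uncounted cannot be derived from the documents. It depends on how often investigators judge a thyroid value without symptoms not medically important, so no percentage is attached.

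Two assumptions apply. TSH and free T4 are taken as outside NCI-CTCAE grading, because Appendix 18.3 gives them no grade; if they were gradable, the grading rule would be the one missed. The laboratory paragraph of protocol 8.5.3.1 is read as the specific rule, prevailing over the parenthesis about hematology and serum chemistry in the same section.

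**What to change.** In SAP 15.3, add TSH and free T4 to the existing low/normal/high shift summaries (baseline category to above normal, and to below normal, during the on-treatment period), by dose level/cohort. State whether aPTT, PT and INR are CTCAE-gradable, then add them to the grade shift tables (with rows in Appendix 18.3) or to the low/normal/high tables accordingly. Keep the listing. A combined row for TSH high with free T4 low, and the reverse, would be useful but is optional; neither document calls for it.

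If the sponsor prefers listing only, SAP Section 7 should declare and justify that choice, and the opening rule of 15.3 should be narrowed to match. That would reconcile the text but leave the by-cohort counts missing.

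The cost is a few lines of SAP wording and one or two extra tables. No new data are needed: the tests are already scheduled, protocol 7.4.3 requires sites to supply local normal ranges, and SAP 15.3 already converts values and ranges to standard units.
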